## **A Motivational Training Program for Secondary Physical Education Teachers Based on the Circumplex Model: A Study Protocol of a Randomized Controlled Trial.**

### **Abstract**

**Introduction:** In most Self-Determination Theory (SDT) research, improving (de)motivating teaching styles enables numerous benefits for students and teachers, although there is less evidence on the latter. Although the recent circumplex model provides a fine-grained picture of the different (de)motivating teaching styles (i.e., autonomy support, structure, control, and chaos) that physical education (PE) teachers can use in their lessons, no previous motivational training programs have been based on this model. Moreover, all SDT-training programs have been implemented through different group sessions, but individual sessions have not also been delivered.

**Objective:** This study outlines the protocol of a motivational training program, derived from the circumplex model, designed to enhance (de)motivating teaching styles among PE teachers. Consequently, this program seeks to improve motivational variables and influence (mal)adaptive outcomes in both teachers and students.

**Design:** A randomized controlled trial design with a mixed-method approach.

**Participants:** At least 16 secondary PE teachers will be assigned to either an experimental group or a control group, together with part of their students.

**Intervention:** The training program comprises four face-to-face group sessions and two follow-up sessions (one individual and one group sessions). PE teachers will learn how to support autonomy and provide structure, as well as to be less controlling and chaotic towards students. Over a period of approximately five months, teachers will implement these motivational strategies during their PE classes.

**Outcome measures:** Different (de)motivating teaching styles, motivational variables, and (mal)adaptive outcomes will be assessed in both PE teachers and their students at three distinct

points: before the training program (T1), during the intervention (T2) and at the end of the intervention (T3). Additionally, two discussion groups involving all experimental PE teachers will be held (one following the training program and another at the end of the intervention).

**Conclusion:** The results from this study could be useful for developing motivational training programs for in-service PE teachers.

**Trial registration: (AÑADIR)**

**Keywords:** circumplex approach, motivating styles, professional development, self-determination theory, psychological needs, motivation.

## Introduction

Physical Education (PE) teachers hold a pivotal role in guiding students through their learning process. Drawing on Self-Determination Theory (SDT; Ryan & Deci, 2020), teachers' (de)motivating style, referred to as "the interpersonal sentiment and behaviour that teachers rely on during instruction to motivate students to engage in and benefit from learning activities" (Reeve et al., 2014, p. 94), is a crucial element in the teaching process. Recent research suggests that PE teachers employ a diverse array of teaching behaviours in their educational practice (Burgueño, García-González, et al., 2024). Autonomy, competence, and relatedness-supportive teaching behaviours (i.e., need-supportive teaching behaviours) have been positively related to students' autonomous motivation and adaptive outcomes in PE, while the opposite is true for autonomy, competence, and relatedness-thwarting behaviours (i.e. need-thwarting behaviours) (Vasconcellos et al., 2020; White et al., 2021). Consequently, continuous development teaching (CDT) programs, based on SDT (Ryan & Deci, 2017), has increased in the last years. These SDT-training programs, mainly focused on autonomy-supportive strategies, revealed positive effects on students' perceptions of (de)motivating teaching behaviours and motivational outcomes (Vasconcellos et al., 2020). Over the past decade, SDT-training programs have also demonstrated positive effects on teachers' self-perceptions of certain antecedents, support for autonomy and structure, and various motivational and (mal)adaptive outcomes (Reeve & Cheon, 2021). However, additional research is required, as most studies have not focused on reducing need-thwarting behaviours.

Recently, grounded in SDT (Ryan & Deci, 2017), the circumplex model (Aelterman et al., 2019) offers a detailed view of the different (de)motivating teaching styles (i.e., autonomy support, structure, control, and chaos) that teachers can adopt in their classes. This circumplex model delineates eight teaching approaches across these four teaching styles (Aelterman et al., 2019; Escrivá-Boulley et al., 2021). To develop the most effective

interventions, it is crucial for researchers to understand the effectiveness of motivational training programs, not only in terms of the four (de)motivating teaching styles but also across the eight specific teaching approaches. Yet, no existing motivational training programs have incorporated this new circumplex approach. This mixed-method study sets out to expand existing knowledge by describing a protocol for a motivational training program based on the circumplex model, aimed at enhancing (de)motivating teaching styles, as well as (mal)adaptive outcomes among PE teachers and their students.

### ***Self-Determination Theory: The Importance of Basic Psychological Needs in Teaching***

According to SDT (Ryan & Deci, 2017), PE teachers need to satisfy the three basic psychological needs (i.e., autonomy, competence, and relatedness) in teaching to experience well-being and feel fulfilled in their job. However, it has been established that these needs can also be frustrated (Vansteenkiste et al., 2020). Autonomy satisfaction is linked with PE teachers' sense of making their own decisions and implementing their ideas in lessons, while autonomy frustration arises from feelings of compulsion to teach in prescribed ways and experiencing pressure in work-related tasks. Competence satisfaction involves PE teachers' perception of success and effectiveness in their PE lessons, whereas competence frustration refers to experiencing feelings of ineffectiveness and failure in their teaching-related tasks. Lastly, relatedness satisfaction is experienced by PE teachers when they feel connected and integrated with colleagues and students, while relatedness frustration occurs when they feel isolated and excluded in their work environment (Ryan & Deci, 2017; Vansteenkiste et al., 2020). According to SDT, teachers' need satisfaction and frustration can be influenced by several antecedents including contextual factors, personal factors, and perceptions of others' behaviours and motivation (Haerens et al., 2016; Matosic et al., 2016). Moreover, in alignment with SDT, these PE teachers' need-based experiences significantly influence their well-being and play a crucial role in the (de)motivating teaching styles they adopt during PE

lessons. Previous SDT-based research (Slemp et al., 2020), indicates that teachers' need satisfaction is positively associated with different adaptive outcomes (e.g., well-being, job satisfaction, engagement, etc.), and need-supportive teaching behaviours towards students. However, teachers' need frustration has been positively related to maladaptive outcomes (e.g., distress, burnout, etc.) and need-thwarting teaching behaviours towards students. Therefore, addressing certain antecedents of (de)motivating teaching styles could enhance teachers' need satisfaction and reduce their frustration, consequently facilitating the adoption of motivating teaching behaviours.

### ***A Fine-Grained Picture of (De)Motivating Teaching Styles: A Circumplex Model***

The circumplex model offers a deeper and detailed perspective of the four teaching styles that a PE teacher can employ in his/her lessons (Aelterman et al., 2019). These styles are categorized along two axes: one horizontal, indicating whether the style supports or thwarts students' needs, and one vertical, reflecting the degree of the directiveness exhibited by the PE teachers. Each teaching style is further divided into two distinct approaches, culminating in a total of eight specific teaching approaches (Aelterman et al., 2019).

On the one hand, the first motivating teaching style, characterized by low directiveness and high need-supportive, is termed autonomy support. PE teachers who demonstrate a tone of receptivity and flexibility to accommodate the preferences and interests of their students provide an autonomy-supportive environment (Vansteenkiste et al., 2019). Autonomy support can emerge by a participative (i.e., PE teacher provides students with choices and decision-making power) and an attuning teaching approach (i.e., PE teacher fosters students' interests, accepts expressions of negative affect, and explains the relevance of each activity performed). The second motivating teaching style, characterized by high directiveness and high need-supportive, is termed structure (Aelterman et al., 2019). Structure involves PE teachers adopting attitudes oriented towards progress and process, always

considering the ability levels and the needs of each student (Vansteenkiste et al., 2019). The structuring style is displayed by a guiding (i.e., PE teacher provides students with helpful guidelines and encouragement for successful task completion) and a clarifying teaching approach (i.e., PE teacher communicates the goals and expectations of the lessons to the students) (Escriva-Boulley et al., 2021).

On the other hand, the first demotivating teaching style, characterized by high directiveness and high levels of need-thwarting, is termed control. It refers to those PE teachers who exert pressure on students to think, feel, and behave in specific ways (Vansteenkiste et al., 2019). This controlling style can be expressed by a demanding (i.e., PE teacher imposes mandatory actions on their students and administer punishment or threats if they fail to comply) and a domineering teaching approach (i.e., PE teacher uses manipulative strategies such as inducing shame, disapproval, or even humiliation to comply with their requests) (Burgueño, Abós, et al., 2024). The second demotivating teaching style, characterized by low directiveness and high levels of need-thwarting, is termed chaos. It refers to those PE teachers who adopt a laissez-faire approach, characterized by their unpredictable and inconsistent behaviour (Vansteenkiste et al., 2019). Chaotic style is expressed by an abandoning (i.e., after multiple failed attempts, the PE teacher resigns and leaves the students to fend for themselves) and an awaiting teaching approach (i.e., PE teachers do not plan lessons extensively as they prefer to wait and see how things unfold) (Aelterman et al., 2019).

Previous studies based on SDT and the circumplex model (Burgueño, Abós, et al., 2024; García-Cazorla et al., 2024) have shown that teachers who have their needs satisfied implement autonomy-supportive (i.e., participative and attuning approaches) and structuring styles (i.e., guiding and clarifying approaches) in their PE, while those teachers who have their needs frustrated, use controlling (i.e., demanding and domineering approaches) and

chaotic styles (i.e., abandoning and awaiting approaches). According to SDT, the adoption of these (de)motivating teaching styles/approaches by PE teachers may elicit various motivational consequences for students.

### ***Influence of (De)Motivating Teaching Approaches on Students' Motivational Outcomes***

Grounded in the circumplex model, a growing body of research examines the relationship between (de)motivating teaching styles/approaches and students' motivational outcomes. For example, Burgueño, Abós, et al. (2024) demonstrated that students' perceptions of autonomy-supportive (i.e., participative and attuning) and structuring (i.e., guiding and clarifying) styles from PE teachers are positively related to students' needs satisfaction, but also the clarifying approach is negatively associated with students' need frustration. Diloy-Peña et al. (2024) also showed that those students who perceived autonomy-supportive and structuring styles and approaches reported higher values in positive PE experiences, learning in PE, and intention to participate in physical activity (PA). Conversely, Burgueño, Abós, et al. (2024) showed that controlling (i.e., demanding and domineering approaches) and chaotic (i.e., abandoning and awaiting approaches) styles are positively associated with students' needs frustration, but also the domineering and abandoning approaches are negatively associated with students' need satisfaction. Additionally, comprehensive SDT-based research in PE indicates that students' need satisfaction is positively related to autonomous motivation and positive behavioral, affective, and cognitive outcomes, while students' need frustration is positively related to controlled motivation, amotivation, and various maladaptive outcomes (Vasconcellos et al., 2020). Consequently, given the associated benefits for students, SDT-training programs aimed at improving PE teachers' motivating teaching style have increased in recent years.

### ***Previous SDT-Training Programs for PE Teachers and Added Value of this Study.***

SDT-training programs have predominantly concentrated on autonomy-supportive strategies, revealing positive effects on students' perceptions of their PE teachers' (de)motivating teaching styles/approaches, as well as on motivational outcomes in PE lessons (Vasconcellos et al., 2020). A previous review of SDT-training programs also suggested that PE teachers can benefit from participating in these programs, although more research is needed to examine their effects on a wide range of outcomes (Reeve & Cheon, 2021). However, there are very few SDT-training programs that examine their effects on both students and teachers. For example, Cheon et al. (2020), showed that PE teachers who participated in an eight-hour, three-session face-to-face SDT-training program, focused on provided structure in an autonomy-supportive way, showed improvements across all assessed variables (i.e., teacher-reported autonomy support and structure, teaching efficacy, intrinsic instructional goals, harmonious passion, job satisfaction, and relationship satisfaction with students). Moreover, students also perceived improvements in autonomy and structure support, autonomy and competence satisfaction, and outcomes such as classroom engagement, skill development, anticipated PE performance, and future intention to do PA. It is noteworthy that in most of these SDT training programs, the effects on teachers have only been assessed after they implemented the strategies with the students (Aelterman et al., 2013). Gaining insight into teachers' perspectives both before the training, immediately after the SDT-training program, and upon completion of the entire intervention, could also enhance the acceptance, sustainability, and scalability of the program. To achieve this, employing a qualitative methodology could build on existing findings, providing greater justification for the results obtained (in addition to quantitative).

To the best of our knowledge, no previous motivational training programs have been designed based on the circumplex model. This model can guide the teaching approaches associated with each of the (de)motivating styles and provide a better understanding of the

potential effects of the program on each of the eight teaching approaches. In the educational domain, only three programs to date have examined the effects of SDT-training programs on (de)motivating teaching styles using the Situations-in-School Questionnaire (SIS; an instrument to assess the eight teaching approaches proposed by the circumplex model) (Cheon et al., 2020; Conesa et al., 2023; Jang et al., 2023). However, none of these programs have specifically examined the effects of all the eight teaching approaches proposed by the circumplex model. In addition, few SDT-training programs have focused on reducing controlling and chaotic teaching styles. Since teachers may combine need-supportive and need-thwarting approaches (Burgueño, García-González, et al., 2024), it seems necessary for these programs to also focus on reducing these behaviors.

The characteristics, content, and implementation mode of the SDT-training programs also appear to be crucial factors to consider. To date, all SDT-training programs have been implemented through different group sessions with PE teachers. However, different person-centered studies have indicated that each PE teacher may exhibit a very different (de)motivating teaching style profile (Burgueño, García-González, et al., 2024). For instance, one teacher might employ both autonomy-supportive and structuring styles, alongside a controlling style. Conversely, another teacher might use autonomy-supportive behaviours while lacking structure, resulting in a chaotic classroom environment. Therefore, it seems necessary that at least part of the motivational training program be individualized to the (de)motivating teaching profile and personal characteristics of each teacher. The use of observational methodology in teacher' own classes has emerged in recent years as a solution to provide constructive and individual feedback through videos (Bouten et al., 2023). However, to date, it has only been used in SDT-training programs to examine intervention fidelity and/or to assess possible changes in the (de)motivating teaching styles (Reeve & Cheon, 2021). Combining a brief initial theoretical component with a more extensive

practical part (i.e., microteaching) has been previously identified as essential for applying what has been learned in contexts as close to reality as possible (Aelterman et al., 2013). Ultimately, the adoption of a congruent style, where trainers implement the program using (de)motivating teaching styles has also been positively perceived by PE teachers. This approach allows them to observe real-life examples of how to implement these strategies effectively (Aelterman et al., 2013). Moreover, in line with SDT, it could lead to an immediate effect on the teachers' need satisfaction during the training that has been positively associated with effectiveness and feasibility beliefs in terms of autonomy support and structure, as well as teachers' intentions to apply the proposed strategies (Aelterman et al., 2016).

Finally, while previous studies have considered gender as a covariate to analyze the effects of SDT-based interventions, gender differences in study variables are seldom reported for both teachers and students. Given prior SDT-related research indicating that (de)motivating teaching behaviours may be perceived differently by boys and girls students (White et al., 2021) and male and female teachers (García-Cazorla et al., 2024), it is crucial to determine whether the intervention is equally effective for both genders to mitigate any potential gender-related inequities.

To extend previous knowledge, this mixed-method study describes the protocol of a motivational training program, based on the circumplex model, aimed at improving (de)motivating teaching styles/approaches among PE teachers. The first hypothesis suggests that the features of the motivational training program will be positively perceived by PE teachers (H1). We also hypothesize that experimental school female and male teachers will perceive improvements in several antecedents, autonomy and competence satisfaction/frustration at work, (de)motivating teaching styles/approaches, and (mal)adaptive outcomes at least at the end of the intervention implementation toward students (H2). Finally,

both boys and girls from experimental groups will perceive improvements in their PE teachers' (de)motivating teaching styles/approaches, autonomy and competence satisfaction/frustration in PE, and adaptive outcomes in PE lessons (H3).

## **Materials and methods**

### ***Context, design, and randomization***

[figure not shown]
This study will be carried out in a northeast region of Spain [details masked for review process]. PE is mandatory for every secondary school student in Spain. Each student receives two 50-minute coeducational PE lessons per week. Spanish Secondary PE teachers are expected to teach between 18 and 21 hours per week. Typically, the annual teaching plan of PE teachers includes approximately six to eight distinct teaching units per year. These units encompass various content types such as individual, cooperative, and interactive sports and games, as well as body expression, health-related fitness, and outdoor activities, all of which are outlined in the PE curriculum. The academic year lasts from September to June, divided into three terms, each separated by a holiday period (i.e., Christmas and Easter).

A randomized controlled trial design with a mixed-method approach will be carried out. PE teachers agreeing to participate in the trial will be randomly assigned to either the experimental or the control group. Randomization will be conducted using the digital tool available at <https://echaloasuerte.com/>. To prevent contamination of the experimental condition, schools will only participate in one group (i.e., experimental or control). Subsequently, at least two groups of students from each PE teacher will be randomly selected.

This study will comprise two phases: 1) a teacher-training phase and 2) an implementation phase with students. It should be noted that the training program will continue with some individual and group sessions during the implementation phase. Since teachers' and students' perceptions of (de)motivating teaching styles and approaches and other study variables require several months for greater accuracy in their perceptions, the

training program will not start until the second term of the academic year (for more details see Figure 1).

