### ***Participants and recruitment***

At least 16 secondary PE teachers, eight in the experimental group and eight in the control group, along with their respective students, will be expected to participate in this study. The maximum number of participating teachers will be capped at 20, due to the limited human resources of the research team. PE teachers will select at least two classroom groups comprising at least 14 students each to invite to participate in this study. Eligible students will be those aged 12 to 17 years in secondary schools. Participation will be voluntary and anonymous.

Various social media platforms (i.e., Instagram, Twitter, and WhatsApp) and other communication methods (i.e., email) will be used for teachers' recruitment. An informative poster will be launched, detailing the target sample, content, aims, and training program dates. This poster will also include two links (QR code): one with a document providing further information and another to registration through a brief Google Forms questionnaire. Regarding the additional information document, it is important to note that it will detail a more comprehensive overview of the objectives, the different phases of the program, inclusion criteria, the requirements that each teacher must accept to participate, and the

teaching skills that will be developed during the training program. Teachers with further inquiries can contact the research team via email or phone. The registration period will last approximately 21 days.

Once the interested PE teachers have registered, various inclusion criteria will be considered for the final selection: 1) Being an in-service PE secondary school teacher for the entire academic year; 2) Attending 100% of the training program sessions; 3) Fill in a short questionnaire at the end of each session of the training program, as well as fulfilling questionnaires of the study variables three times; 4) Allowing the recording of two PE lessons; 5) Participating in two focus groups, one at the end of the training program and one at the end of the study, and 6) Not participating in other training sessions related to PE instruction during the program. Moreover, the inclusion criteria for students will be: 1) Authorization from parents or legal guardians; 2) Completion of questionnaires of the study variables three times; 3) Regular participation in PE lessons.

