### ***Analysis plan***

#### ***Quantitative analyses***

Firstly, the effects of the four sessions of the training program on the study variables assessed in teachers will be examined. The overall mean for each of the 11 variables perceived by PE teachers about the quality of the training program (e.g., interaction, innovation, interest, intelligibility, etc.) will also be calculated, representing the mean across the different sessions. A repeated measures analyses of variance (ANOVA) will be used to assess PE teachers' global appreciation of 11 variables related to the quality of the training program (e.g., interaction, innovation, interest, intelligibility, etc.) across the sessions of the training (i.e. within-subject analyses). Accordingly, each of the training sessions will be introduced as an independent variable (i.e. within-subject factor) and repeated measures of the PE teachers-related variables will be entered sequentially as dependent variables.

Secondly, the effects of the intervention implementation in PE lessons on study variables for both teachers and students will also be examined. Levene and Kolmogorov–Smirnov tests will be used to ensure the equality of variances and normal data distribution, respectively ( $p > .05$ ). Cronbach's coefficient will be calculated for each study variable across the three measurements. To examine the effects of the intervention on study variables, a  $3 \times 2$  (time x condition) repeated measures multivariate analysis of covariance (MANCOVA) will be performed for both teachers and students. Age, gender, teaching experience, type of school (public or private), and school location (rural or urban) will be introduced as covariates among teachers, while age, gender, and school grade level will be introduced as covariates among students. Subsequently, to examine intragender differences of the intervention on study variables, a  $3 \times 2 \times 2$  (time x condition x gender) repeated measures MANCOVA will be performed for both teachers and students. The same covariates will be entered as previously analysis, excluding gender. Multiple paired t-tests with Bonferroni correction will be calculated to determine between-group (i.e., experimental-control group) and within-group (i.e., pre-post) differences. Cohen's criteria will be used as indicators of small (.01), moderate

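### No balancing of the 16 to 20 teachers on gender, school type or school location is described, although the teacher analysis relies on all three and the student model omits two

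*Protocol*

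**What the plan says.** Under Context, design, and randomization, the protocol makes the teacher the unit of allocation: "PE teachers agreeing to participate in the trial will be randomly assigned to either the experimental or the control group". The method is one sentence: "Randomization will be conducted using the digital tool available at" a named website. The one restriction described is meant to prevent contamination: "schools will only participate in one group (i.e., experimental or control". Stratification, blocking, matching and minimisation are not mentioned anywhere.

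Participants and recruitment gives the numbers: "At least 16 secondary PE teachers, eight in the experimental group and eight in the control group", and "The maximum number of participating teachers will be capped at 20". How the draw secures eight per arm is not stated.

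Quantitative analyses then relies on the factors that the draw does not balance. For teachers, "Age, gender, teaching experience, type of school (public or private), and school location (rural or urban) will be introduced as covariates among teachers". A second model is a 3 × 2 × 2 design: "time x condition x gender) repeated measures MANCOVA will be performed for both teachers and students". Student covariates are age, gender and grade only. The Introduction regards it as crucial to learn whether the programme works equally for both genders, and the second hypothesis names female and male teachers.

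**The concern.** The analysis treats gender, school type and school location as important enough to adjust for, and makes teacher gender a factor. The allocation, as described, protects none of them. All three are known before the draw and are already due to be collected by questionnaire.

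Three things are at stake:

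- **Precision of the teacher comparison.** With 16 teachers, the intercept, condition and five covariates leave 16 − 7 = 9 error degrees of freedom. Imbalance makes the adjustment costlier.
- **The teacher gender analysis.** It splits 16 to 20 teachers into four cells, so a cell may hold one teacher or none.
- **Credibility of the student comparison.** It carries the third hypothesis but does not adjust for school type or location, so a visible rural/urban or public/private difference between arms would have no planned answer.

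**Working it through.** The protocol gives no figure on balance to reproduce, so the check is what a draw without balancing would produce.

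**Inputs from the protocol.** 16 teachers at 8:8, or 20 at the cap, taken as 10:10.

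**Assumed inputs.** The number K of teachers in the smaller category of each factor is not given, so a range is shown. Each teacher is treated as separately allocable. The three factors are treated as independent in the joint calculation.

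**1. Gender cells.** There are C(16,8) = 12,870 equal-size allocations. The number that put k of the K minority teachers in the experimental arm is C(K,k) × C(16−K, 8−k).

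- K = 4, k = 0 to 4: 495, 3,168, 5,544, 3,168, 495. One or none in an arm: 2 × (495 + 3,168) / 12,870 = 57%. None: 990 / 12,870 = 7.7%.
- K = 5: the outer terms are 165 and 1,650. One or none: 2 × 1,815 / 12,870 = 28%. None: 330 / 12,870 = 2.6%.
- K = 6: the outer terms are 45 and 720. One or none: 2 × 765 / 12,870 = 12%. None: 90 / 12,870 = 0.7%.
- K = 7 and K = 8: one or none in 4% and 1%.
- 20 teachers at 10:10, K = 4, 5, 6: one or none in 58%, 30% and 14%.

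**2. Imbalance on at least one of the three factors.** The chance that the arms differ by 3 or more teachers on one factor is 7.7%, 28.2%, 11.9% and 13.2% for K = 4, 5, 6 and 8 of 16. (For even K the difference is always even, so 3 or more means 4 or more.) The joint chance is 1 − Π(1 − p):

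- Minority counts 8/4/4: 1 − 0.868 × 0.923² = 26%
- 8/6/4: 1 − 0.868 × 0.881 × 0.923 = 29%
- 8/8/8: 1 − 0.868³ = 35%
- 6/5/5: 1 − 0.881 × 0.718² = 55%
- 20 teachers: 39% for 10/6/6 and 45% for 10/10/10

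With a stricter threshold of 4 or more, the scenarios tried with 16 teachers give 18% (8/5/5) to 35% (8/8/8).

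**3. Room for a restricted draw.** For 6/5/5, the chance that all three factors differ by at most 1 is 0.392 × 0.718² = 0.202, or about 2,600 of the 12,870 allocations. For 8/8/8 it is 0.381³ = 0.055, or about 710. A constrained draw is therefore still a real randomisation.

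**4. What a small cell does.** The 3 × 2 × 2 teacher model has four condition-by-gender cells and four remaining covariates, so 16 teachers leave 16 − 8 = 8 error degrees of freedom. Error is pooled, so a one-teacher cell can be estimated but very imprecisely. An empty cell makes the interaction inestimable.

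**The case against.** The strongest reply is that simple randomisation needs no balancing to be valid. Chance imbalance does not bias the design. Everyone is measured at T1, and the test of interest is time by condition, so a stable level difference between school types does not enter that contrast; only differential change would. The teacher model also adjusts for the three factors. All of this stands, and it limits the harm to precision, credibility and the gender cells.

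The size of the problem also depends on a mix that the documents do not give. With genders at 8 and 8, the risk of a cell of one or none is 1%. Nor does balance rescue the gender analysis: with 5 of 16, the best split is 3:2.

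Some stronger readings are tempting but unsupported:

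- A reader might infer that a public web draw cannot be repeated or audited. The documents do not say what the tool can do; they only describe no seed or record.
- A reader might infer that a single-teacher cell defeats the analysis. It does not, because error is pooled.
- A reader might infer that imbalance carries directly into every comparison. The T1 measures and the teacher covariates argue against that.
- A reader might expect unequal arm sizes. The protocol expects eight per arm, so the point concerns the make-up of the arms.

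**Conclusion.** The point holds as a recommended change to the allocation; it does not show the trial to be invalid. The protocol describes no balancing on three factors that its own teacher analysis uses, and the student model leaves two of them out.

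With 16 teachers at 8:8, at least one factor differs by 3 or more teachers in about 26% to 55% of draws. An arm has one or no teacher of the minority gender in 57%, 28%, 12%, 4% and 1% of draws for 4, 5, 6, 7 and 8 of 16. An empty cell is much rarer: 7.7%, 2.6% and 0.7% for 4, 5 and 6 of 16.

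These figures rest on assumed mixes, equal arms, independent factors and separately allocable teachers. If several teachers come from one school, there are fewer independent units and imbalance becomes more likely. That no restriction exists is read from the protocol's silence, since the tool itself cannot be checked from the documents.

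**What to change.** - **Registration.** Ask teacher gender, school type and school location on the existing registration form, and record each teacher's school.
- **Draw.** After the registration period of about 21 days closes, make one scripted and seeded draw in R, which the sample size calculation already used. Draw from the equal-size allocations that keep each school in one arm and differ by at most 1 on each factor. If the school rule prevents this, come as close as it allows, with gender taking priority when not all three can be met. Archive the script and seed.
- **Analysis.** Keep the three factors in the teacher analysis, and add school type and location to the student model.
- **Text.** State this in Context, design, and randomization, and amend the student covariates in Quantitative analyses.

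The cost is three form items, a few lines of code and a single draw that waits until registration has closed. The protocol should also say that the teacher gender comparison will remain thin even when balanced.
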